6.3 Safety/Tolerability

Safety outcomes will be reported separately as incidences (n, incidence rate with 95%CI) in total and by intervention group based on the safety analysis set. Incidence rates and 95%CI will be based on poisson regression models that account for the different observation periods for each participant. Group comparisons will be done using incidence rate ratios and 95%CI. Results of safety analysis will be interpreted and discussed thoroughly also for minor group differences, since statistically significance is not of importance here.

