1.4 Study Design

The TrainStim-Home trial is a randomized, double-blind, placebo-controlled monocenter study. The experimental group receives a six-session cognitive training intervention over two weeks, accompanied by tDCS over the left dorsolateral prefrontal cortex (DLPFC). The intervention of the control group consists of the same six-session cognitive training combined with sham stimulation.

Random allocation to experimental and control groups, respectively, will be performed with a 1:1 ratio. Stratified block randomization will be used. Strata will be chosen according to age (60-70 and 71-80 years) and initial performance in the letter updating task (≤ 5 , $\geq 5/25$ correctly recalled lists). After successful completion of telephone screening and baseline assessment (defined as meeting all eligibility criteria) and giving written informed consent, participants will be divided into four groups according to the age and performance strata. For the randomization we will use the blockrand package

in R¹.

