2.1 Definitions

The **full analysis set** will consist of all participants who received at least one day of intervention. In case participants withdraw informed consent after baseline assessment, they will be considered as screening failures and therefore will not be included in the full analysis set. The **per protocol analysis set** comprises all subjects who successfully completed two-thirds of the home-based sessions (thus fulfilling the criterion for feasibility). Safety measures will be assessed during tDCS intervention and all participants who received at least one day of intervention will be included according to their actual treatment in **the safety analysis set**.

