Abbreviations: T1-T6, training 1-6; FU, follow-up-assessment; V0-V9, visits 0-9; CERAD Plus, The Consortium to Establish a Registry for Alzheimer's Disease, neuropsychological test battery, German version, extended to CERAD Plus with the Trail Making Test A + B and Phonematic Fluency (S-Words); tDCS, transcranial direct current stimulation; PANAS, positive and negative affect schedule. All measures were acquired on site or at the respective participants home, except for screening which was done via telephone. *assessed only at the end of each training week (V4 and V7).

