4.4 Safety Outcomes

Safety parameters are assessed via self-report questionnaire every third day of training (V4, V7). The questionnaire was adapted from Antal et al. (2017) and includes intensity ratings with regard to itching, pain, burning, warmth/heat, metallic/iron taste, fatigue/decreased alertness and other sensations.

5 Handling of missing values

Primary outcome of this trial is the feasibility of the intervention. For the primary outcome no missing value imputation will be done, since missing information is related to non-adherence of the participants. Secondary efficacy outcome analyses will be done using complete data without any imputation, due to the small sample size and the exploratory framework of the study.

6 Statistical analyses

For all analyses (including the analysis of the primary outcome) appropriate descriptive statistics (absolute score, mean, standard deviation, median, interquartile range, absolute and relative frequencies) depending on the scale and distribution of the outcome variable will be presented.

Statistical analyses will be divided to analyze

- 1. feasibility
- 2. training effects on letter updating task (at post and 1 month follow-up)
- 3. transfer effects on n-back task (at post and 1 month follow-up)

Training and transfer measures will be corrected for performance at pre-assessment.

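### Section 6.3 fits Poisson rates over observation time to sensation ratings taken only at V4 and V7, with no within-person handling and no rule for participants who stop before V4

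*SAP*

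**What the plan says.** Section 6.3 sets the method: "Incidence rates and 95%CI will be based on poisson regression models that account for the different observation periods for each participant". It continues: "Group comparisons will be done using incidence rate ratios and 95%CI". Results are to be given overall and per arm. Even small differences between arms are to be discussed, because statistical significance is said not to matter for safety.

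Section 4.4 describes the data: "Safety parameters are assessed via self-report questionnaire every third day of training (V4, V7". The questionnaire "includes intensity ratings with regard to itching, pain, burning, warmth/heat, metallic/iron taste, fatigue/decreased alertness and other sensations", which makes six named items and one open item. The footnote to Table 1 confirms the schedule: "assessed only at the end of each training week (V4 and V7".

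Section 2.1 defines the safety set: "all participants who received at least one day of intervention will be included according to their actual treatment".

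The linear mixed models in section 6.2 carry a random intercept for repeated measures within a person. Section 6.3 names nothing comparable. Section 5 covers missing data for the primary outcome and the secondary efficacy outcomes, but not for safety.

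**The concern.** A Poisson rate describes events that can occur and be recorded at any moment of follow-up, with variance equal to the mean. Here a sensation can be recorded only when a questionnaire is filled in, at two fixed visits. For one sensation a person's count is capped at 2. Two reports from the same person are likely to be alike, and so are reports of different sensations. The cap pulls the true variance below the Poisson value and the clustering pushes it above, so the model-based interval is right only where the two happen to cancel.

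The denominator has a related problem. A person who stops after V2 or V3 belongs to the safety set but never reaches a scheduled questionnaire. If exposure is time or sessions on treatment, that person enters the denominator and cannot enter the numerator.

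What is at stake is the description of tolerability. With 15 per arm and an announced intention to discuss small differences, the estimates and their intervals are all a reader has to judge by.

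**Working it through.** Section 6.3 states no figure, so there is none to reproduce.

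**Inputs from the SAP.** 15 per arm (section 1.5); two safety questionnaires (section 4.4); seven items (section 4.4); six planned sessions, V2 to V7 (section 1.4, Table 1).

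**Assumed, because the SAP gives no values.** Probability p that an item is reported on a questionnaire; within-person correlation rho; number k of 15 who stop before V4.

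**1. Variance.** Let a person give m yes/no reports with common probability p and pairwise correlation rho. The variance of the count is m·p·(1−p)·[1+(m−1)·rho]. Poisson assumes m·p. The ratio of true to assumed variance is (1−p)·[1+(m−1)·rho].

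- One sensation, m = 2: the ratio is (1−p)(1+rho). The interval is too narrow only if rho exceeds p/(1−p), that is 0.25 at p = 0.2 and 0.43 at p = 0.3.
- All seven items at both visits, m = 14: the ratio is (1−p)(1+13·rho).

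**2. Coverage of the nominal 95% interval for a rate ratio whose true value is 1.** Beta-binomial simulation, 15 per arm, 40,000 runs per row. Runs with no event in one arm were dropped (under 1% in every row shown). The robust column uses a participant-level robust standard error with t on 28 degrees of freedom.

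| Count | p | rho | Variance ratio | Poisson coverage | Robust coverage |
|---|---|---|---|---|---|
| One sensation | 0.2 | 0.3 | 0.8 × 1.3 = 1.04 | 97.1% | 97.8% |
| One sensation | 0.3 | 0.3 | 0.7 × 1.3 = 0.91 | 96.8% | 97.0% |
| One sensation | 0.7 | 0.3 | 0.3 × 1.3 = 0.39 | 99.8% | 97.1% |
| One sensation | 0.7 | 0.6 | 0.3 × 1.6 = 0.48 | 99.5% | 97.5% |
| Pooled, 14 reports | 0.2 | 0.1 | 0.8 × 2.3 = 1.84 | 85.4% | 95.1% |
| Pooled, 14 reports | 0.3 | 0.1 | 0.7 × 2.3 = 1.61 | 88.0% | 95.4% |
| Pooled, 14 reports | 0.2 | 0.3 | 0.8 × 4.9 = 3.92 | 67.4% | 94.7% |
| Pooled, 14 reports | 0.3 | 0.3 | 0.7 × 4.9 = 3.43 | 70.5% | 95.4% |

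For one sensation the interval is near nominal, or too wide when the sensation is common. For a pooled count it is too narrow.

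**3. Participants who stop before V4.** They have done one session (V2) or two (V2, V3). Suppose exposure is counted in sessions and everyone else completes six. If k of 15 in an arm stop after s sessions, the arm's rate is multiplied by 6(15−k) / [6(15−k) + k·s].

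- k = 1, s = 1: 84/85 = 0.988, a fall of about 1%.
- k = 4, s = 2: 66/74 = 0.892, a fall of about 11%.

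If the offset is the number of questionnaires returned, these people have zero exposure and the dilution disappears. If the same number stop equally early in both arms, the factor is the same in both and cancels from the rate ratio.

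**The case against.** The strongest reply is that section 6.3 is under-specified rather than wrong. It does not rule out a robust variance. Its observation periods could be read as the periods covered by a completed questionnaire, and then early stoppers contribute nothing. No score summed over sensations is defined. The instruction to report overall and by arm most naturally means both arms together, not a sum over items. For single sensations at moderate prevalence the planned interval is close to nominal. Much of this stands: it limits the size of the problem and makes the pooled result conditional.

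It does not remove the mismatch. The SAP names a model, a denominator type and an effect measure, and these do not describe bounded reports repeated at two visits. It handles clustering explicitly for the efficacy tasks and leaves it out here.

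Three stronger readings are tempting and not supported.

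- *The intervals are simply wrong, and could create or hide a difference between arms.* The error has no single direction. The serious undercoverage needs pooling, which the SAP does not state, and no safety decision is tied to significance.
- *Early stoppers count as full event-free persons.* With two-week exposure for everyone, the fall would be 1/15 to 4/15, or 7-27%, for 1 to 4 of 15. Section 6.3 says exposure differs between participants, so this is not the planned estimator.
- *Early stoppers left because of sensations.* Nothing in the SAP says so.

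A fair point against the fix is that the proportion with any report ignores whether a person returned one questionnaire or two. The number returned should therefore be shown beside it.

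**Conclusion.** The point holds as a mismatch between the stated safety model and the way the data arise. Model-based Poisson intervals would be near nominal to too wide for one sensation: coverage is about 97% at 20-30% prevalence and correlation 0.3, and over 99% at 70% prevalence. They would be clearly too narrow, with coverage of about 67-88%, if reports were pooled over sensations at 20-30% prevalence per item and correlations of 0.1-0.3. All prevalences and correlations are assumptions, and the pooled figures apply only if pooling is done.

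The early-stopper effect is real only if exposure means time or sessions on treatment. It is then small with session-based exposure, and it distorts the rate ratio only if early stopping differs between arms. It also presumes that no reports outside the two questionnaires are counted; section 4.4 lists none.

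The consequence is misleading precision in tolerability results. The feasibility conclusion is not affected. The change is worth making because it is cheap and replaces a poorly fitting method.

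**What to change.** Amend section 6.3 as follows.

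1. State which rating counts as a report. For each sensation, give the number and proportion of assessed participants with at least one report, by arm, with Agresti-Coull intervals, as section 6.1 already does for feasibility. Show the number of questionnaires returned per arm.
2. If rate ratios are kept, use a variance robust to clustering by participant and take questionnaires returned as the offset. Say whether any count is pooled over sensations.
3. List safety-set participants with no questionnaire separately, by arm, with their reason for stopping, instead of letting them enter as event-free exposure. No offset can recover sensations that were never asked about, so they need to be visible.

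The cost is a few lines of SAP text and one software option, with no new data collection. The downside is small: intervals for any pooled total become wider, and the denominator must be shown for each table.

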6.4 Planned subgroup analyses

We will conduct subgroup analyses regarding participant's cognitive reserve, operationalized by their education years and their commitment to the intervention, operationalized by the number of successful conducted training sessions. Subgroups will be achieved through median splits.

All subgroup analyses will be done within an exploratory framework, using descriptive analyses.

6.5 Example table for the description of baseline characteristics Table 2. Baseline characteristics of the study sample.

	All	TDCS group	Sham group
	n =	n =	n =
Age (years)			
Gender (n, % female)			
Education (years)			
GDS			
Semantic fluency			
BNT (max. 15)			
MMSE (max. 30)			
Word list learning			
Total (max. 30)			
Trial 1 (max. 10)			
Trial 2 (max. 10)			
Trial 3 (max. 10)			
Word list retrieval (max. 10)			
Word list intrusions			
Figure copying (max. 11)			
Figure retrieval (max. 11)			
Phonematic fluency			
Trail-making test			
Part A (sec)			
Part B (sec)			
Digit-span			
Forward			
Backward			
Data are shown as the mean (SD) or n(9	%). GDS, Geriatric I	Depression Scale. BNT, Bos	ton Naming Test. MMSE, Mini

Mental Status Examination. RT, reaction time.

7. References

- Antal A et al. (2017) Low intensity transcranial electric stimulation: Safety, ethical, legal regulatory and application guidelines. Clin Neurophysiol 128:1774-1809.
- Berryhill ME (2017) Longitudinal tDCS: Consistency across Working Memory Training Studies. AIMS Neuroscience 4:71-86.
